6.1.8 Week 20 Telephone Visit

This visit will take place 140 ± 3 days after the Baseline Visit via telephone.

6.1.9 Week 24 Visit or Early Termination Visit

Participants should be instructed to skip the morning dose of study drug on the day of the study visit. Study drug should not be taken until after study visit procedures are complete.

The Week 24 Visit will take place in-person 168 ± 7 days after the Baseline Visit. The following procedures will be performed at either the Week 24 Visit or the Early Termination Visit for the regimen schedule:

- Home Spirometry
- ALSAQ-40
- CNS Bulbar Function Scale
- Collection of plasma samples for verdiperstat PD biomarkers (MPO protein and activity) and a plasma PK sample
- Voice Recording
- Uninstall Smartphone App
- Dispense IP (only if continuing in OLE)
- Remind participant to bring IP to the next visit

For participants rolling into the OLE, all participants should be instructed to follow the dose escalation scheme.

- After all Week 24 procedures are completed, administer a single 300 mg tablet of verdiperstat. Participants should stay at the clinic for approximately 30 minutes for observation.
- Dispense study drug to last for the next 4 weeks.
- Participants should be instructed:
 - To ingest 300 mg QD of BHV-3241 for the rest of Week 1.
 - To ingest 300 mg BID of BHV-3241 starting at the beginning of Week 2. Participants should take the study drug twice a day; dosing in the morning and evening approximately 12 hours apart.
 - If tolerability issues are experienced with 300 mg QD or 300 mg BID dosing, the titration schedule may be modified (see Section 5.3.2).
 - To ingest 600 mg BID of BHV-3241 starting at the beginning of Week 3 and through the remainder of the 52-week OLE. Participants should take the study drug twice a day; dosing in the morning and evening approximately 12 hours apart.

For participants NOT rolling into the OLE:

A Follow-up Safety Call should be scheduled approximately 28 days after last dose of study drug to collect clinical status information.

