² The last visit for the open-label extension will be at Week 52. Participants who withdraw consent or terminate early (prior to Week 52) from the study will be asked to be seen for an in-person Early Termination Visit and should have the same procedures as the Week 52 visit.

³ Participants who continue into the OLE and then early terminate will be asked to complete an Early Termination Visit and Follow-Up Safety Call as described in the body of this RSA.

⁴ Participants will have a Follow-up Safety Call approximately 28 days after the last dose of study drug. At this call, information on clinical status should be collected.

⁵ Vital signs include weight, systolic and diastolic pressure, respiratory rate, heart rate and temperature.

⁶ Clinical safety labs include hematology (CBC with differential), complete chemistry panel, liver function tests, thyroid function (TSH) and urinalysis. Serum pregnancy testing will occur in women of child-bearing potential at the Master Protocol Screening Visit and as necessary during the study. Pregnancy testing is only repeated as applicable if there is a concern for pregnancy.

⁷ Myeloperoxidase protein and activity, and plasma concentrations of verdiperstat will be measured. For each sample, the time of the last verdiperstat dose prior to sample collection, time of the last meal prior to sampling, and time of the PD/PK sample collection should be reported on the CRF.

⁸ Administer first dose of investigational product (IP) only after Week 24 procedures are completed. Participants should take the first dose of IP while in the office/clinic on the day of the Week 24 visit and stay at the clinic for approximately 30 minutes post-dose for observation.

⁹ From start to end of Week 1, participants will ingest 300 mg QD of verdiperstat QD. From start to end of Week 2, participants will ingest 300 mg BID of verdiperstat BID. Starting with Week 3 and continuing to Week 52, participants will ingest 600 mg BID of verdiperstat BID.

¹⁰ Participants should be instructed to skip the morning dose of study drug on the day of the study visit – at OLE Weeks 16, 28 and 52. Study drug should not be taken until after study visit procedures are complete.

¹¹ Visit may be conducted via phone or telemedicine with remote services instead of in-person if this is needed to protect the safety of the participant due to a pandemic.

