5.3.2 Dosage Modification

Participants will be instructed on the dosing regimen. If tolerability issues are experienced during the dosage titration period with the 300 mg QD and/or 300 mg BID doses (or matching placebo), the titration schedule may be extended (e.g., up titration to the next dosage level delayed by an additional week). Potential tolerability issues may include sudden, clinically significant changes from baseline in symptoms of presyncope, syncope, orthostatic hypotension, or falls that are not otherwise explained. The SI must consult with the Medical Monitor if he or she believes that a change to the dosage titration schedule is warranted; and, the SI must document any such changes to the dosage titration schedule.

During the full dose period of the study, it is anticipated that all participants will receive either verdiperstat 600 mg BID or matching placebo BID. If participants have difficulty tolerating verdiperstat 600 mg BID or matching placebo BID dosing, the SI may permit the participants to switch to verdiperstat 300 mg BID or matching placebo BID dosing (and document this change in the participant's records). Potential tolerability issues may include those listed above as well as clinically significant laboratory abnormalities (i.e., thyroid and renal function) that are not otherwise explained. Down titration to verdiperstat 300 mg BID or matching placebo BID will only be allowed to address tolerability issues and only with Medical Monitor approval. If a participant is down titrated to the 300 mg BID dose, they may be allowed to retry the 600 mg BID dose (re-challenge), if deemed appropriate by the SI and Medical Monitor. Only two re-challenges are allowed. Any such changes must be documented. If a switch to verdiperstat 300 mg BID or matching placebo BID dosing does not result in acceptable tolerability, then dosing should be discontinued.

Dosage modification should be considered if a participant experiences one of the following:

- a. Clinically significant changes in frequency and/or severity from baseline in symptoms of presyncope, syncope, orthostatic hypotension, and/or falls that are not explained by disease progression or intercurrent illness and not able to be adequately treated with symptomatic pharmacological and non-pharmacological treatments, based on the judgement of the SI.

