6.2.1 Week 2 Telephone Visit - OLE

This visit (via telephone) will take place 14 ± 3 days after the Week 24 visit. The procedures listed in the SoA should be performed including:

- Assess and document AEs and concomitant medications, including Key Study Events (see section 10.3 of Master Protocol)
- Assess compliance and tolerance to this dose titration schedule
 - If tolerability issues are experienced with 300 mg QD or 300 mg BID dosing, the titration schedule may be modified (see Section 5.3.2).
- Instruct participants on appropriate dosing
 - Starting at the beginning of Week 3, to ingest 600 mg BID of verdiperstat and continue taking this dose through the remainder of the 52-week OLE
- Remind participant to bring in IP to the next visit

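### The OLE dosing text steps every entrant up to 600 mg BID at Week 3, with no exception for a participant held at 300 mg BID because 600 mg BID was not tolerated

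*Protocol*

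**What the plan says.** Three places in the Protocol set the OLE dose.

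- Section 6.1.9: "For participants rolling into the OLE, all participants should be instructed to follow the dose escalation scheme". The last step there is "To ingest 600 mg BID of BHV-3241 starting at the beginning of Week 3 and through the remainder of the 52-week OLE".
- Section 6.2.1, the OLE Week 2 call: "Starting at the beginning of Week 3, to ingest 600 mg BID of verdiperstat".
- Footnote 9 of the OLE Schedule of Activities: "Starting with Week 3 and continuing to Week 52, participants will ingest 600 mg BID of verdiperstat BID".

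The tolerability clause attached to this titration, in Section 6.1.9 and again in Section 6.2.1 and OLE footnote 1, reads "If tolerability issues are experienced with 300 mg QD or 300 mg BID dosing, the titration schedule may be modified (see Section 5.3.2").

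Section 5.3.2 covers a participant who cannot tolerate 600 mg BID. Reduction to 300 mg BID "will only be allowed to address tolerability issues and only with Medical Monitor approval". After a reduction, "they may be allowed to retry the 600 mg BID dose (re-challenge), if deemed appropriate by the SI and Medical Monitor", and "Only two re-challenges are allowed". It adds recovery conditions: Grade 2 or less after Grade 3 or 4 hypothyroidism, and Grade 1 or less after other toxicity of Grade 3 or higher or an intolerable side effect attributed to the drug. If 300 mg BID is not tolerated either, dosing stops.

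Section 6.2 opens the OLE to anyone who completed the blinded phase on drug. It does not require the full dose.

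**The concern.** Section 5.3.2 treats the return to 600 mg BID as a decision to be made for the individual. The OLE text treats it as a routine step for everyone. A site that follows the OLE text as written would reverse a reduction the Medical Monitor had approved, without the judgement, recovery check or re-challenge count that Section 5.3.2 asks for.

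For a participant from the active arm, this is re-exposure to a dose already found intolerable. The reasons for reduction named in Section 5.3.2 include presyncope, syncope, orthostatic hypotension, falls, and thyroid or renal laboratory abnormalities. For a participant from the placebo arm it is a first exposure to verdiperstat, and ordinary titration is reasonable. The OLE text does not tell a site how to distinguish the two.

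**Working it through.** The plan gives no figure to reproduce. The check compares the texts and then bounds the number affected.

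**Can the participant reach the OLE?** Yes. Section 5.3.2 allows continued treatment at 300 mg BID, and Section 6.2 requires only that the blinded phase was completed on drug.

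**Does the OLE tolerability clause catch this participant?** Not as worded. It is triggered by problems at 300 mg QD or 300 mg BID. Someone still on drug at 300 mg BID at Week 24 is expected to tolerate that dose, since Section 5.3.2 would otherwise have stopped dosing. For an active-arm participant the trigger is therefore not expected to occur before the step to 600 mg BID.

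**Does any other OLE step hold the dose?** The Week 2 call reviews adverse events and tolerance, but at a dose already expected to be acceptable. The OLE schedule puts safety laboratory tests at Day 0 and Week 4, with none at the Week 2 call, and does not make the Week 3 step depend on any result.

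**Is this just the blinded-phase wording again?** Section 6.1.3 gives a similar Week 3 instruction, but before any exposure to 600 mg BID. The OLE instruction comes after the reduction.

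**Number affected.** Planned allocation is 120 active and 40 placebo (RSA Summary). The reduction rates below are assumptions, with every reduced participant entering the OLE:

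| Assumed share of active arm held at 300 mg BID | Active participants re-exposed |
|---|---|
| 1% | 120 × 0.01 = 1.2 |
| 5% | 120 × 0.05 = 6 |
| 10% | 120 × 0.10 = 12 |

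**Arm split.** Let k be the reduction rate on active divided by that on placebo, with equal OLE entry by arm. The placebo share of those held at 300 mg BID is 40 / (120k + 40) = 1 / (3k + 1).

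| k (assumed) | Placebo share | Active share |
|---|---|---|
| 1 | 1/4 = 25.0% | 75.0% |
| 2 | 1/7 = 14.3% | 85.7% |
| 3 | 1/10 = 10.0% | 90.0% |

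**Re-challenge limit.** An active-arm participant who used both re-challenges has had 1 + 2 = 3 exposures to 600 mg BID verdiperstat. The OLE step would be the fourth exposure. If it counts as a re-challenge, it is the third against a limit of two. The placebo counterpart has had none.

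**The case against.** The strongest reply is that Section 5.3.2 already governs. It is not limited to a phase, and the Protocol generally states a default dose in the schedule and leaves departures to Section 5.3.2. Section 5.3.1 is just as categorical about 600 mg BID for the rest of the study, and nobody would read it as cancelling an approved reduction. On this reading, harm requires a site to ignore a documented decision. A site can reasonably read the Protocol this way. However, the OLE text is a fresh instruction to all entrants, issued after the reduction, and its own pointer to Section 5.3.2 is confined to problems at the lower doses. The site is left to choose between a general rule and a later, specific one.

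Other points stand and limit the weight of the concern:

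- Uniform titration suits placebo participants, and no OLE text provides for unblinding at Week 24. Section 5.3.2, though, applies its conditions to verdiperstat and matching placebo alike.
- Safeguards remain: the restart at 300 mg QD, the Week 2 call, renewed reduction with Medical Monitor approval, and the reductions or holidays in Sections 5.4 and 9.1. Renewed reduction acts only after re-exposure.
- Section 5.9.1.3 reports no syncope on verdiperstat in the earlier studies of extended-release formulations, although dizziness and orthostatic hypotension did occur.
- The Protocol does not say whether the limit of two carries into the OLE, so exceeding it is an ambiguity and not a demonstrated breach.
- The Master Protocol and Manual of Procedures were not available and may contain the missing instruction.

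**Conclusion.** The concern holds, within the RSA. Three OLE instructions send every entrant to 600 mg BID, while Section 5.3.2 makes that step conditional for a participant reduced for intolerance. These rules conflict, and following the OLE text literally is the less safe course for active-arm participants.

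The number is unknown and probably small. The figures of about 1, 6 and 12 rest on assumed reduction rates and full OLE entry. They also assume that every site escalates without consulting the Medical Monitor, so they are upper values for each rate. Under the assumed ratios, 75% to 90% of those held at 300 mg BID would come from the active arm. This is a matter of OLE safety and conduct; the 24-week primary and secondary analyses are not touched. It should be fixed because the correction is simple and the re-exposure avoidable.

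**What to change.** Add one sentence to each of Section 6.1.9, Section 6.2.1 and OLE footnote 9: a participant at 300 mg BID at Week 24 because of a Section 5.3.2 reduction titrates to 300 mg BID, and moves to 600 mg BID only once the SI and Medical Monitor agree and the Section 5.3.2 recovery conditions are met.

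State also that the Medical Monitor takes earlier blinded re-challenges into account. After two, the step needs explicit Medical Monitor approval. It should be neither automatic nor barred outright, because the participant may have been on placebo. The rule works by dose held, so it needs no unblinding.

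An optional clarification in Section 5.4 would say whether re-escalation after more than 14 days off drug stops at the dose held before the interruption. SAP Section 2.7 defers to the RSA and needs no change.

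The cost is three sentences and a site memo. No new procedure or tablet strength is needed, since 300 mg BID is one 300 mg tablet twice a day. The downside is that some verdiperstat-naive participants, 10% to 25% of those held at 300 mg BID under the assumptions above, wait at 300 mg BID until the step is approved.

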6.1.10 Follow-Up Safety Call

Participants will have a Follow-Up Safety Call 28±7 days after their last dose of study drug. Only those participants NOT continuing on in the Open Label Extension will have the Follow-Up Safety Call following the end of their participation in the placebo-controlled portion of the trial. The following procedures will be performed:

- Assess and document AEs, including Key Study Events (*see section 10.3 of Master Protocol*)

6.1.11 Process for Early Terminations

Participants who early terminate from the study and do not complete the protocol per ITT will be asked to be seen for an in-person Early Termination Visit and complete a Follow-Up Safety Call. If a participant is not able to be seen in-person, safety assessments and others that can be conducted remotely should be performed.

The in-person Early Termination Visit should be scheduled as soon as possible after a participant early terminates. If the participant early terminates during the placebo-controlled portion of the Regimen, all assessments that are collected at the Week 24 in-clinic visit should be conducted. The Follow-Up Safety Call should be completed approximately 28±7 days after the last dose of study drug. If the participant terminates early during the OLE period, all assessments that are intended for collection at the OLE Week 24 in-clinic visit should be conducted. The Follow-Up Safety Call should be completed approximately 28±7 days after the last dose of IP.

If the Early Termination Visit occurs approximately 28±7 days after the last dose of study drug, the information from the Follow-Up Safety Call can be collected during the Early Termination Visit, and a separate Follow-Up Safety Call does not need to be completed. If the in-person Early Termination Visit does not occur within 28±7 days of the last dose of study drug, the Follow-Up Safety Call should occur approximately 28±7 days after the last dose of study drug and the Early Termination Visit will be completed after the Follow-Up Safety Call.

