For participants who early terminate from the placebo-controlled phase, an in-person Early Termination Visit and a Follow-up Safety Call should be conducted. At the Early Termination Visit the same procedures as described for the Week 24 visit should be conducted. At the Follow-up Safety Call, information on clinical status should be collected.

For participants who early terminate from the OLE, an in-person Early Termination Visit and a Follow-up Safety Call should be conducted. At the Early Termination Visit the same procedures as described for the Final visit should be conducted. At the Follow-up Safety Call, information on clinical status should be collected.

Total Planned Trial Duration

For participants completing only the placebo-controlled Treatment Period of the study, the planned amount of time for participation in the trial is 34 weeks, or about 8 months. This duration assumes a 6-week screening window, a 24-week placebo-controlled treatment period, and a 28-day safety follow-up period for those participants who do not enter the OLE. Participants will complete approximately 10 study visits during the placebo-controlled period of the study.

SCHEDULE OF ACTIVITIES – 24-WEEK PLACEBO-CONTROLLED PHASE

As per the Schedule of Activities (SOA) below, visits must occur every 4 weeks and will be alternatively clinic-, phone-, or telemedicine-based, as applicable. There is a maximum 24-week duration of placebo-controlled treatment for a Regimen.

| Activity | Master Protocol or Regimen-Specific | Master Protocol Screening ¹ | Regimen Specific Screening ¹ | Baseline | Week 2 ² | Week 4 ^{18,19} | Week 8 ^{18,19} | Week 12 | Week 16 ^{18,19} | Week 20 | Week 24 or Early Term. Visit ^{3, 18} | Follow-up Safety Call ^{3,4} |
|---|-------------------------------------|--|---|----------|---------------------|-------------------------|-------------------------|-----------|--------------------------|------------|---|--------------------------------------|
| | | Clinic | Clinic | Clinic | Phone | Clinic | Clinic | Phone | Clinic | Phone | Clinic | Phone |
| | | -42 to -1 Days | -41 to 0 Days | Day 0 | Day 14 ±3 | Day 28 ±7 | Day 56 ±7 | Day 84 ±3 | Day 112 ±7 | Day 140 ±3 | Day 168 ±7 | 28±7 days after last dose |
| Written Informed Consent – Placebo-controlled Period ⁵ | Master | X | X | | | | | | | | | |
| Written Informed Consent - OLE | Regimen | | | | | | | | X | | | |
| Inclusion/Exclusion Review | Master | X | X ⁶ | | | | | | | | | |

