|--|----------------|----------------------|----------------------|----------------------|----------------------|--------------------------|------------------------|------------------------|--|---------------------------------------|
| Activity | Week 24 Visit | Week 2 ¹ | Week 4 ¹¹ | Week 8 ¹¹ | Week 12 | Week 16 ^{10,11} | Week 20 | Week 24 | Week 28 ^{10,11} and Q12 weeks | Follow-up Safety Call ^{3,4} |
| | Clinic | Phone | Clinic | Clinic | Phone | Clinic | Phone | Phone | Clinic | Phone |
| | Day 0 | Day 14 _{±3} | Day 28 _{±7} | Day 56 _{±7} | Day 84 _{±3} | 112 _{±7} days | 140 _{±3} days | 168 _{±3} days | Q12 weeks _{±14} days | 28 _{±7} days after last dose |
| Vital Signs ⁵ | X | | X | X | | X | | | X | |
| Slow Vital Capacity | X | | X | X | | X | | | X | |
| Home Spirometry | | | X | X | | X | | | X | |
| Muscle Strength Assessment | X | | | | | | | | | |
| ALSFRS-R | X | | X | X | X | X | X | X | X | |
| ALSAQ-40 | X | | | | | | | | X ¹⁴ | |
| CNS bulbar Function Scale | X | | | X | | X | | | X | |
| 12-Lead ECG | X | | X | | | | | | X ¹³ | |
| Clinical Safety Labs ⁶ | X | | X | X | | X | | | X | |
| Biomarker Blood Collection | X | | | | | X | | | X ¹² | |
| Verdiperstat (BHV-3241 specific PD biomarkers ⁷) | X | | | | | X | | | X ¹² | |
| PK Blood Collection ⁷ | X | | | | | X | | | X ¹² | |
| Biomarker Blood Collection | X | | | | | X | | | X ¹² | |
| Biomarker Urine Collection | X | | | | | X | | | X ¹² | |
| Concomitant Medication Review | X | X | X | X | X | X | X | X | X | |
| Adverse Event Review | X | X | X | X | X | X | X | X | X | X |
| Columbia-Suicide Severity Rating Scale | X | | X | X | | X | | | X | |
| Administer/Dispense Investigational product | X ⁸ | | X | X | | X | | | X ¹⁵ | |
| Drug Accountability/Compliance | X | X ¹⁶ | X | X | X ¹⁶ | X | X ¹⁶ | X ¹⁶ | X | |
| Dose Escalation | | X ⁹ | | | | | | | | |

HEALEY ALS Platform Trial
 Regimen-Specific Appendix B, Verdiperstat
 Version 6.0 , 02-December-2021
 CONFIDENTIAL

¹ At the end of Week 2, an assessment of compliance and tolerance to this dose titration schedule will be conducted. The assessment will be conducted by phone. If tolerability issues are experienced with 300 mg QD or 300 mg BID dosing, the titration schedule may be modified (see Section 5.3.2).

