¹² Biomarker Blood Collection, Biomarker Urine Collection and all regimen-specific samples will occur at OLE Weeks 16, 28 and 52 only.

¹³ 12-Lead ECG is performed at OLE Weeks 4 and 52 only

¹⁴ The ALSAQ-40 is performed at OLE Weeks 28 and 52 only

¹⁵ Investigational product is not administered at the participant's final in-clinic visit at the completion of the OLE.

¹⁶ Drug accountability will not be performed at phone visits. A drug compliance check-in must be held during phone visits to ensure participant is taking drug per dose regimen and to note any report of missed doses.

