3 RSA DESIGN

This study is a multicenter, randomized, double-blind, 2-arm placebo-controlled parallel-group study designed to evaluate the efficacy and safety of verdiperstat in a population of participants with ALS. The study is planned to consist of a Screening phase lasting a maximum of approximately 6 weeks (42 days) and a randomized double-blind treatment phase of approximately 24 weeks (see Figure 1). It is anticipated that the Randomization phase will include a dose titration period of approximately 2 weeks followed by a full dosage period of approximately 22 weeks. Participants completing 24 weeks of treatment with verdiperstat or placebo will be eligible to continue to an Open-label Extension Phase (OLE) which will include an additional 52 weeks of dosing. Approximately 160 participants in total are planned to be randomized in a 3:1 ratio to receive either verdiperstat 600 mg BID, or matching placebo BID. The assessments for each visit are outlined in the Schedule of Activities (SoA).

Figure 1. Regimen Specific Appendix Schematic

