6.2 Open Label Extension (OLE)

Participants who have completed the placebo-controlled portion of the trial on drug, will be eligible to continue in the Open Label Extension. The OLE of the study will continue until verdiperstat is approved and available in the United States, or Biohaven Pharmaceuticals terminates development of verdiperstat for ALS.

Modifications to OLE Schedule

Designated visits in the Schedule of Activities for the OLE (i.e. Week 4, Week 8, Week 16, Week 28, and Week 40) may be conducted via telemedicine (or phone if telemedicine is not available) with remote services instead of in-person if needed to protect the safety of the participant due to a pandemic or other reason. If a planned in-clinic visit is conducted via telemedicine (or phone if telemedicine is not available) with remote services, only selected procedures will be performed. Instructions on how to document missed procedures are included in the Manual of Procedures.

In addition to the procedures in the Master Protocol that should be conducted during the phone or telemedicine and remote visits, the following regimen-specific procedures should be completed:

- Home Spirometry
- CNS Bulbar Function Scale (Week 8 and 16 only).

Blood samples for Week 16 PK and PD analysis and the Week 4 and 28 ECGs are **not** collected during the remote visits by the home health agency and this should be recorded as such in the applicable source documentation and EDC.

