6.2.7 Week 24 Telephone Visit – OLE

This visit will take place 196 ± 3 days after the Week 24 Visit of the placebo-controlled portion of the trial via telephone. The procedures listed in the SoA should be performed.

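### Section 6.1.11 of the Protocol ties early exit from the OLE to an in-clinic OLE Week 24 visit that the schedule makes a telephone call, and the OLE is both 52 weeks long and open-ended

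*Protocol*

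**What the plan says.** **Exit visit.** Three places in the Protocol give the assessments for someone who terminates early from the OLE.

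- Section 6.1.11: "all assessments that are intended for collection at the OLE Week 24 in-clinic visit should be conducted".
- OLE Schedule of Activities, footnote 2: such participants "should have the same procedures as the Week 52 visit".
- RSA Summary, Follow-up Duration: "At the Early Termination Visit the same procedures as described for the Final visit should be conducted".

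Section 6.2.7 is headed "Week 24 Telephone Visit – OLE".

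**Duration.** Section 3 describes an OLE "which will include an additional 52 weeks of dosing". Section 6.2 says: "The OLE of the study will continue until verdiperstat is approved and available in the United States", or until the company ends development in ALS. The RSA Summary agrees with Section 6.2. Section 6.2.8 sets visits every 12 weeks after Week 28 and states no end.

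**ECG.** Footnote 13 of the OLE schedule: "12-Lead ECG is performed at OLE Weeks 4 and 52 only". Section 6.2, in its text on remote visits, refers to ECGs at OLE Weeks 4 and 28. Section 5.9.1.3 says that ECGs will go on being monitored in this study.

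**The concern.** These are operative instructions on what is checked when a participant leaves the OLE, and on how long participants are treated and followed. Section 6.1.12 lists adverse events and laboratory abnormalities among the reasons for mandatory discontinuation, so some early leavers will be people for whom exit safety data matter most. If sites (about 60 are planned) resolve the conflict differently, exit data will differ by site, and some exits may lack vital signs, safety labs, ECG and C-SSRS.

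The duration conflict raises a second question: which assessments apply after Week 52. The ECG footnote, the sampling footnote and the dosing text all stop at Week 52, while two passages let the OLE run beyond it.

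**Working it through.** No sample size, power or alpha figure is involved. The check is a cross-reading of the Protocol, with counts from the OLE Schedule of Activities and calendar arithmetic.

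**1. What kind of visit is OLE Week 24?** The mode row of the OLE schedule reads "Clinic | Phone | Clinic | Clinic | Phone | Clinic | Phone | Phone | Clinic | Phone". The ten columns are, in order: the Week 24 Visit (Day 0), Weeks 2, 4, 8, 12, 16, 20 and 24, Week 28 with the 12-weekly visits, and the follow-up call. OLE Week 24 is the eighth, which is Phone. The first column, also labelled Week 24, is Clinic, but it is the last placebo-controlled visit and serves as OLE Day 0.

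**2. Is the day consistent?** 24 × 7 = 168 days, as in the schedule. Section 6.2.7 gives 196 days, and 196 = 28 × 7, the day of the Week 28 clinic visit. The text for this visit therefore conflicts with the schedule as well.

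**3. What would each exit rule collect?**

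- OLE Week 24 column: 4 procedures (ALSFRS-R, concomitant medication, adverse events, compliance check).
- Week 28 and 12-weekly column, read at Week 52: 16 distinct procedures, counting the duplicated biomarker-blood row once and leaving out drug dispensing.
- Difference: 16 − 4 = 12. These are vital signs, SVC, home spirometry, ALSAQ-40, CNS-BFS, ECG, safety labs, biomarker blood, biomarker urine, PD, PK and C-SSRS.
- Sections 8.2 and 8.3 do not require PK and PD samples at early discontinuation. Without them, 12 − 2 = 10.
- Four of the ten are direct safety checks: vital signs, ECG, safety labs and C-SSRS.

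The OLE schedule has no column called Final. That label means Week 52 only if the OLE ends there.

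**4. How long is the OLE?**

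- Fixed at 52 weeks or Week 52: OLE schedule footnotes 2 and 9, and Sections 3, 4.3, 6.1.9 and 6.2.1. Taking the two footnotes together, that is five places.
- Open-ended until approval or end of development: RSA Summary and Section 6.2, two places.
- Visit series with no stated end: the 12-weekly column and Section 6.2.8. From Week 28 it runs 28 + 12 = 40, 40 + 12 = 52, then 64, 76 and so on.

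**5. What is scheduled after Week 52 if the OLE is open-ended?**

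- Continuing every 12 weeks: vital signs, safety labs (including liver tests and TSH, footnote 6), C-SSRS and adverse event review, with SVC, ALSFRS-R and others.
- Not scheduled: ECG (footnote 13), and PK, PD and biomarker samples (footnote 12).

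The ECG result rests on footnote 13, which the Week 28 ECG in Section 6.2 contradicts.

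**6. Does the document hierarchy settle it?** SAP Section 1 makes the Master Protocol and the RSA authoritative on matters other than analysis and ranks the RSA highest. Here the RSA conflicts with itself, so the ranking gives no answer.

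**The case against.** The strongest reply is that sites would not be misled. Section 6.1.11 asks for an in-person visit and, where that is not possible, for the safety and other assessments that can be done remotely. A four-item telephone check sits badly with that text. A site looking in the OLE schedule for an in-clinic Week 24 visit would find the Day 0 column, which includes vital signs, SVC, safety labs, ECG and C-SSRS. A reader might infer from Section 6.1.11 that participants will certainly leave without these checks; the documents do not support that. What stands is that the section requires attendance but takes its assessment list from a visit that does not exist as described. It also cites the placebo-controlled Week 24 clinic visit separately, so OLE Week 24 reads naturally as something else.

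Second, the three exit rules reduce to two on the 52-week reading, because Final and Week 52 are then the same visit. That is right. In the extracted table no row or column carries the marker for footnote 2; it may have been lost in extraction.

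Third, a reader might infer that liver and thyroid monitoring lapses after Week 52. It does not: on the open-ended reading the 12-weekly labs continue. The ECG gap remains. Section 5.9.1.3 says that the data on extended-release formulations show no clear evidence of significant cardiovascular abnormalities, but it also says that an effect cannot be excluded and commits to continued ECG monitoring. Ending PK, PD and biomarker sampling at Week 52 can be a deliberate sampling choice and is not counted as a defect.

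**Conclusion.** The point holds as two internal contradictions in the current RSA.

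- **Exit assessments.** On one literal reading a site would perform 4 of the 16 procedures marked for Week 52. It would omit 10 required ones, four of them direct safety checks. This could happen; it is not certain to.
- **Duration.** The OLE is both 52 weeks and open-ended. On the open-ended reading the one safety assessment left without a schedule after Week 52 is the ECG, and the ECG schedule is itself inconsistent.

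The SAP covers only the placebo-controlled period, so the primary and secondary efficacy analyses, power and type I error are unaffected. The conclusion assumes that the schedule tables were extracted correctly and that the Master Protocol and Manual of Procedures, which were not available, do not already resolve the conflict. No view is taken on which exit visit, duration or ECG schedule is right. The change should be made because the instructions bear on participant safety and the correction is nearly free.

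**What to change.** 1. Reconcile Section 6.1.11, footnote 2 of the OLE schedule and the Follow-up Duration text of the RSA Summary to one named OLE visit that exists in the schedule. Correct the day or the label in Section 6.2.7 so that it agrees with the schedule.
2. Reconcile the two OLE durations across the RSA Summary, Sections 3, 4.3, 6.1.9, 6.2, 6.2.1 and 6.2.8, and OLE schedule footnotes 2 and 9. Carry the decision into the 12-weekly column.
3. Reconcile footnote 13 with the ECG weeks named in Section 6.2 and with the monitoring commitment in Section 5.9.1.3, and state what applies after Week 52 if the OLE continues.

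The clinical choices are for the sponsor. The cost is RSA wording only, with no change to the SAP, the sample size or the placebo-controlled schedule.
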